5.6.2. Other Protocol Restrictions

Participants will be encouraged to avoid strenuous or prolonged exercise, as well as saunas, steam baths, and sunbathing or other prolonged ultraviolet exposure (eg, in a tanning salon) from the screening evaluation until completion of the last study visit, as these activities are known to affect certain clinical laboratory test parameters (eg, creatine kinase [CK]) and will provide false indicators of a potentially treatment-related toxicity.

Upon every visit to the clinic, each participant will be questioned as to their compliance with the above protocol restrictions. If a participant is unable to comply with any of the restrictions described above, the participant's continued participation in the study will be reevaluated by the investigator in consultation with the sponsor.

6. STUDY ASSESSMENTS

The study procedures to be conducted for each participant enrolled in the study are presented in tabular form in [Table 1](#), [Table 2](#), and [Table 3](#) and are described in the sections below.

Any deviation from protocol procedures should be noted in the participant's clinical chart and appropriate eCRFs. In addition, the sponsor should be promptly notified of any protocol deviations.

The study sites will not initiate dosing until the following have all been met:

- The IEC or other applicable regulatory agencies have reviewed and approved the study and the informed consent document.
- All requested regulatory documents have been submitted to and approved by Gilead.
- A master services agreement and/or study agreement is executed.
- The study initiation meeting has been conducted by Gilead (or designee).

A study initiation meeting will include but is not limited to a review of the protocol, the IB, investigational product, and investigator responsibilities.

Documentation of the personally signed and dated ICF for each participant, using the study-specific, IEC-approved ICF, is required before initiating the screening process.

6.1. Informed Consent

Written informed consent (Section [9.1.4](#)) must be obtained from each participant before initiation of any screening procedure. After a participant has provided informed consent, the investigator and other study personnel will determine if the participant is eligible for participation in the study (Section [6.3.2](#)).

CCI

The informed consent document is completely redacted, leaving only the label 'CCI' and a large black rectangular area where the text would have been.

6.2. Participant Enrollment and Treatment Assignment

Entry into screening does not guarantee enrollment into the study. In order to manage the total study enrollment, Gilead, at its sole discretion, may suspend screening and/or enrollment at any site or study wide at any time.

It is the responsibility of the investigator to ensure that participants are eligible to participate in the study prior to enrollment and continue to remain eligible throughout the study.

Once the ICF has been obtained, all screening tests and evaluations have been assessed, and study eligibility has been confirmed, participants will be enrolled to receive investigational product on Day 1. Baseline assessments as well as confirmation of negative urine pregnancy tests in women of childbearing potential will need to be completed prior to dosing.

Participants will receive the study treatment assignments as described in Section [5.3](#) and [Table 8](#).

6.3. Instructions for Study Procedures

6.3.1. Adverse Events

From the time informed consent is obtained through the first administration of investigational product, record all SAEs, as well as any AEs related to protocol-required procedures on the AE eCRF. All other untoward medical occurrences observed during the screening period, including exacerbation or changes in medical history, are to be considered medical history. After investigational product administration, report all AEs and SAEs. Evaluation of AEs will occur at the visits shown in [Table 1](#), [Table 2](#), and [Table 3](#). See Section [7](#) for additional details.

6.3.2. Screening Assessments

A sufficient number of participants will be screened to identify the planned number of participants for randomization.

Screening laboratory assessments may be repeated once within 45 days prior to administration of investigational product for exclusionary laboratory values if, in the investigator's opinion, one of the following are met: there is reason to believe the retest value will be within accepted parameters, if the initial value was deemed to be inaccurate or inconsistent with the participant's previous result(s), if the initial value was generated in error (eg, mishandled sample), or there is another relevant extenuating circumstance. In any instance, the site should obtain approval from Gilead prior to repeating the laboratory assessment.

Participants should be instructed to fast (no food or drink, except water), starting from midnight (00:00) or earlier, as appropriate, on the evening prior to the screening visit to ensure an approximate 8-hour fast prior to the fasted blood sample collection the next morning.

The screening assessment will include a review of the inclusion/exclusion criteria (Sections 4.2 and 4.3) and completion of all screening procedures as outlined in [Table 1](#), [Table 2](#), and [Table 3](#). Eligible participants meeting all of the inclusion criteria and none of the exclusion criteria will be instructed on all protocol requirements.

6.3.3. Treatment Assessments

Study procedures and assessments are outlined in [Table 1](#), [Table 2](#), and [Table 3](#).

Sentinel group participants are to be monitored in the clinic for at least 8 hours following the first administration of investigational product. All subsequent doses for the sentinels and all other Phase 1a participants will be monitored in the clinic for at least 4 hours following administration of investigational product. Participants in Cohorts 5 through 7 will be monitored in the clinic for at least 2 hours following the administration of investigational product. Participants may be required to remain in the clinic for additional observation at the discretion of the investigator. At the end of this observation period, participants will need to be assessed for any postinjection reactions and AEs, any reportable events will need to be recorded in the eCRF.

Participants will be contacted by phone on the following days to review protocol restrictions, AEs, any concomitant medication usage, and completion of their participant diaries:

Cohorts 1 and 2: Days 2, 3, 58, and 59.

Cohorts 3, 4, 5, and 6: Days 2, 3, 30, 31, 58, 59, 86, and 87.

Cohorts 7 and 8: Days 2, 3, 30, 31, 58, 59, 86, 87, 114, 115, 142, and 143.

6.3.4. Participant Diaries for Reactogenicity

Participants will be asked to record potential investigational product reactions based on solicited events via a diary for 7 days following each administration of investigational product. Review of participant reactogenicity data will occur at the next visit that is greater than 7 days postdose ([Table 1](#), [Table 2](#), and [Table 3](#)). Solicited events will include, but may not be limited to, temperature, local events of injection-site pain, swelling, erythema, induration, and systemic events of fatigue, fever, arthralgia, myalgia, headache, and nausea. Any reactogenicity event that meets the criteria for AEs based on Section 7.1.1 must be reported in the appropriate eCRF.

6.3.5. Clinical Virology

6.3.5.1. Sample Collection for Antivector Antibody Evaluation

The incidence of antivector antibodies against GS-2829 and GS-6779 may be assessed in samples collected at the time points shown in [Table 1](#), [Table 2](#), and [Table 3](#). Samples that are found to be positive for antivector antibodies may be further characterized.

6.3.5.2. HBV Viral Biomarkers

Phase 1b only: HBV viral biomarkers (HBsAg, HBV DNA, HBV RNA, HBcrAg, and HBeAg) will be collected at the time points indicated in [Table 2](#) and [Table 3](#) and evaluated as needed.

6.3.5.3. Sample Collection for Genomic Sequencing

Phase 1b only: Blood samples from virally suppressed participants will be collected for genomic sequencing and genotyping of HBV at the time points indicated in [Table 2](#) and [Table 3](#) and evaluated as needed.

6.3.6. Sample Collection for Biomarker Evaluation

6.3.6.1. Biomarker Samples to Address the Study Objectives

Biological specimens will be collected from all participants who have provided consent to participate in this study and may be used to evaluate the association of systemic and/or tissue-based biomarkers with investigational product response and dosage selection, and to better understand drug-induced biological pathways and/or HBV biology.

Because biomarker science is a rapidly evolving area of investigation, and AEs in particular are difficult to predict, it may not be possible to prospectively specify all tests that may be done on the specimens provided. The specific analyses will include, but may not be limited to, the biomarkers and assays listed below. The testing outlined below is based upon the current state of scientific knowledge. It may be modified during or after the end of the study to remove tests no longer indicated and/or to add new tests based upon new state-of-the-art knowledge.

Blood samples will be collected to measure biomarkers that will include, but may not be limited to:

- investigational product-induced T-cell responses by IFN- γ ELISpot
- phenotype and function of HBV-specific T-cell and B-cell responses
- peripheral soluble protein (including cytokines, chemokines, and inflammatory markers)
- HBV-targeted antibody responses

Samples will be collected at the time points outlined in [Table 1](#), [Table 2](#), and [Table 3](#). A more detailed breakdown of the biomarker assays is also provided in [Table 4](#), [Table 5](#), and [Table 6](#).

Samples collected for biomarker assessments will be destroyed no later than 20 years after the end of the study or per country requirements (Section [9.1.4](#)).

CCI

6.4. Safety Assessments

Safety will be evaluated throughout the study. Refer to [Table 1](#), [Table 2](#), and [Table 3](#) for a schedule of safety assessments.

6.4.1. Electrocardiogram Assessment

Recording of the ECG will occur at screening ([Table 1](#), [Table 2](#), and [Table 3](#)).

Participants should rest quietly in the supine position for a minimum of 10 minutes prior to each scheduled 12-lead ECG acquisition and should remain in that position until the recording is complete.

The investigator or other qualified individual at the study center will review the ECG for abnormalities.

Collection of additional ECGs for routine safety monitoring at additional time points or days is at the discretion of the investigator based on GCP.

6.4.2. Physical Examination

Physical examinations conducted throughout the study will be a complete physical examination or a symptom-driven physical examination, as outlined in [Table 1](#), [Table 2](#), and [Table 3](#). The complete physical examination conducted at screening will also include the following assessments:

- General appearance, and the following body systems: head, neck, thyroid, eyes, ears, nose, throat, mouth, and tongue; chest (excluding breasts); respiratory, cardiovascular; lymph nodes; abdomen; skin, hair, nails; musculoskeletal; neurological. Genitourinary and breast examinations should not be conducted unless clinically indicated.

- Review medical history, including history of allergies, prior and current use of nicotine or nicotine-containing products, alcohol and illegal/illicit drug use, and prior and current (within 30 days) medication use.

6.4.3. Vital Signs

Vital sign measurements include blood pressure, heart rate, and body temperature and should be collected once participants have been seated or are in the supine position. Participant position for measurement should be kept consistent throughout the study. Refer to [Table 1](#), [Table 2](#), and [Table 3](#) for vital signs collection time points.

6.4.4. Body Mass Index

Height (cm) and weight (kg) will be collected at screening for calculation of BMI for inclusion criteria.

6.4.5. Clinical Laboratory Tests/Assessments

Blood and urine samples for safety evaluations will be collected throughout the study as outlined in [Table 1](#), [Table 2](#), and [Table 3](#).

No fasting or alteration of diet is required for this study, with the exception of fasting prior to the collection of laboratory assessments performed for screening. Participants should be instructed to fast (no food or drink, except water), starting from midnight (00:00) or earlier, as appropriate, on the evening prior to the screening visit to ensure an approximate 8 hour fast prior to the fasted blood sample collection the next morning.

Table 10. Laboratory Analytes

Safety Laboratory Measurements			
Chemistry (Serum or Plasma)	Hematology	Urinalysis	Other Laboratory Measurements
ALP	CBC with differential, and platelets	Color and clarity	Serum pregnancy test
AST		Specific gravity	Urine pregnancy test
ALT		pH	Serum FSH
GGT	Coagulation panel, including prothrombin time, aPTT, and INR	Glucose	Plasma HBV DNA, HBV RNA, HBV surface antigen
Total bilirubin		Protein	HBV surface antibody
Direct and indirect bilirubin		Blood and microscopic (reflex if positive)	HBV core-related antigen
Total protein		Leukocyte esterase and microscopic (reflex if positive)	HBeAg
Albumin			HBeAb
Lactate dehydrogenase			HIV serology
Bicarbonate			HDV antibody
BUN			HCV antibody serology reflex to HCV RNA
Calcium			HBV immunogenicity (IFN- γ ELISpot assay)
Chloride			HBV-1-specific T-cell phenotype and function
Creatinine			Peripheral soluble proteins (including cytokines, chemokines, and inflammatory markers)
Glucose			Antivector immune responses
Hemoglobin A1c			Autoantibodies: ANA, anti-SMA, AMA, and anti-TPO
Phosphorus			
Magnesium			
Potassium			
Sodium			
Lipase			
Total cholesterol			
High-density lipoprotein			
Low-density lipoprotein			
Triglycerides			
CPK/CK			
Uric acid			

ALP = alkaline phosphatase; ALT = alanine aminotransferase; AMA = antimitochondrial antibody; ANA = antinuclear antibody; aPTT = activated partial thromboplastin time; AST = aspartate aminotransferase; BUN = blood urea nitrogen; CBC = complete blood count; CK = creatine kinase; CPK = creatine phosphokinase; DNA = deoxyribonucleic acid; ELISpot = enzyme-linked immunospot assay; FSH = follicle-stimulating hormone; GGT = gamma-glutamyl transferase; HBV = hepatitis B virus; HBeAb = hepatitis B e antibody; HBeAg = hepatitis B e antigen; HCV = hepatitis C virus; HDV = hepatitis D virus; HIV = human immunodeficiency virus; IFN = interferon; INR = international normalized ratio; RNA = ribonucleic acid; SMA = smooth muscle antibody; TPO = thyroid peroxidase

Refer to [Table 1](#), [Table 2](#), and [Table 3](#) for collection time points.

6.4.5.1. Blood Sampling

Blood samples will be collected for the following laboratory analyses:

- Hematology: Hematocrit, hemoglobin, platelet count, red blood cell count, white blood cell count with differential (absolute and percentage), including lymphocytes, monocytes, neutrophils, eosinophils, basophils, and mean corpuscular volume
- Coagulation panel: prothrombin time, activated partial thromboplastin time, and INR
- Chemistry (fasting at screening only; otherwise nonfasting): ALP, AST, ALT, gamma-glutamyl transferase (GGT), total bilirubin, direct and indirect bilirubin, total cholesterol, high-density lipoprotein, low-density lipoprotein, triglycerides, total protein, albumin, lactate dehydrogenase, creatine phosphokinase/CK, bicarbonate, blood urea nitrogen, calcium, chloride, creatinine, glucose, hemoglobin A1c, phosphorus, magnesium, potassium, sodium, uric acid, and lipase.
- Serum pregnancy test for all women of childbearing potential (Note: participants assigned female at birth are considered to be in a postmenopausal state when they are at least 54 years of age with cessation of previously occurring menses for at least 12 months without an alternative cause)
- Follicle-stimulating hormone testing (screening only) for participants assigned female at birth who are younger than 54 years, not on hormonal contraception, and who have stopped menstruating for at least 12 months but do not have documentation of ovarian hormonal failure
- HIV-1, HBV, and HCV testing
- HDV testing (Phase 1b only)

6.4.5.2. Urine Samples

Urine samples will be collected for urinalysis and alcohol and drug screen assessments, which may include alcohol, amphetamines, barbiturates, benzodiazepines, cocaine, marijuana, 3,4-methylenedioxymethamphetamine, methadone, opiates, and phencyclidine at screening and Day 1.

6.4.5.3. Pregnancy Testing

Serum pregnancy testing will be performed at screening and baseline (Day 1). On all dosing days, urine pregnancy testing will be performed in addition to serum testing to confirm pregnancy status for all women of childbearing potential. Pregnancy testing will continue every 28 days posttreatment as shown in [Table 1](#), [Table 2](#), and [Table 3](#) until the end of study follow-up.

For Cohorts 1 to 2, safety follow-up Day 113, Day 169, and Day 197; for Cohorts 3 to 6, safety follow-up Day 141, Day 197, and Day 225; and for Cohorts 7 to 8, safety follow-up Day 169, Day 197, Day 225, Day 253, Day 281, and Day 309 are required only for pregnancy testing for women of childbearing potential. These participants will come to the site and undergo serum pregnancy testing, with the exception of participants who are able to access an at-home urine pregnancy test from the clinical site; these participants may conduct their pregnancy test at home and will be contacted by site staff to confirm the result.

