Number of Participants Planned: Approximately 80 participants are planned for 8 cohorts. of 10 participants each: 50 healthy participants for Phase 1a activities and 30 participants diagnosed with CHB for Phase 1b activities.

Target Population:

Phase 1a: Healthy male and nonpregnant, nonlactating female participants, aged 18 through 60 years, inclusive

Phase 1b: Male and nonpregnant, nonlactating female participants diagnosed with CHB, aged 18 through 65 years, inclusive

Duration of Intervention:

- Cohorts 1 and 2 will receive 2 total doses over 56 days (Days 1 and 57).
- Cohorts 3, 4, 5, and 6 will receive 4 total doses over 84 days (Days 1, 29, 57, and 85).
- Cohorts 7 and 8 will receive 6 total doses over 140 days (Days 1, 29, 57, 85, 113, and 141).
- All participants will be followed for safety for 24 weeks following their last dose of investigational product (through Day 225 for Cohorts 1 and 2; through Day 253 for Cohorts 3, 4, 5, and 6; and Day 309 for Cohorts 7 and 8).

Diagnosis and Main Eligibility Criteria:

Phase 1a: Eligible participants will include those assigned male sex at birth or those who are nonpregnant, nonlactating, assigned female at birth, aged 18 through 60 years inclusive, with a body mass index (BMI) of $\leq 32.0 \text{ kg/m}^2$, with normal or nonclinically significant 12-lead electrocardiogram (ECG) evaluations, and no significant medical history. Participants will also be in good general health as determined by the investigator and have no prior history of hepatitis B virus (HBV) infection as demonstrated with a negative hepatitis B surface antigen (HBsAg) and hepatitis B core antibody test. Participants are prohibited from receipt of any investigational product or vaccine within 3 months of screening (with the exception of influenza and SARS-CoV-2 vaccines, which if needed, should be administered at least 14 days before or after an investigational product administration; participants should be encouraged to receive any needed vaccinations prior to enrollment) and should not receive ongoing therapy with any prohibited medications listed in the protocol.

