Cohort 6: Initiation of Cohort 6 will be determined at the discretion of the SRT based on the evaluation of available safety data through Day 43 (14 days after initial dose of both the investigational products for all participants enrolled in Cohort 4), available safety data from participants enrolled in Cohort 5, and all available safety data from all dosed cohorts, and dosing will be initiated only in the absence of dose-limiting toxicity and/or meeting any prespecified stopping criteria. The duration of this review period may be increased based on the emerging and cumulative safety data.

Cohort 7: Initiation of Cohort 7 will be determined at the discretion of the SRT based on the evaluation of available safety data through 14 days (Day 43) after initial dose of both the investigational products for all participants enrolled in Cohort 4, available safety data from participants enrolled in Cohort 5, and all available safety data from all dosed cohorts. Initiation of the third dose of 2 vector combination therapy will be determined at the discretion of SRT based on the evaluation of the available safety data through Day 99 (14 days after all participants in Cohort 4 have completed the second dose of both investigational products), in addition to all available safety data. The decision on cohort initiation will be based on prespecified criteria agreed upon by the SRT and documented in the SRT charter. The duration of this review period may be increased based on the emerging and cumulative safety data.

CHB = chronic hepatitis B; D = Day; HBV = hepatitis B virus; HP = healthy participant; SRT = Safety Review Team

Figure 2. Schema for Cohorts 1 and 2 (Two Total Doses)

Phase 1a

[figure not shown]
- Cohort 1: Low Doses of GS-2829 or Placebo in HP
- Cohort 2: Low Doses of GS-6779 or Placebo in HP

- GS-2829 or GS-6779 dose or Placebo
- ▲ PBMC for Biomarker Cellular Assays
- ◊ Serum for HBV-Targeting Antibody Measurements
- ✗ Whole Blood for Biomarker Analysis
- HBV Neutralizing Antibody and Antivector Antibody Assessment

** Day 113, Day 169 and Day 197 visits are only required for female participants of childbearing potential

HBV = hepatitis B virus; HP = healthy participant; PBMC = peripheral blood mononuclear cell
Note: A follow-up phone call will be performed on Days 2, 3, 58, and 59.

Figure 3. Schema for Cohorts 3, 4, 5, and 6 (Four Total Doses)

Phase 1a

- Cohort 3: Low Doses of GS-2829 and GS-6779 or Placebo in HP

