- Cohort 4: High Doses of GS-2829 and GS-6779 or Placebo in HP

Phase 1b

[figure not shown]
- Cohort 5: Low Doses of GS-2829 and GS-6779 or Placebo in virally suppressed participants with CHB
- Cohort 6: High Doses of GS-2829 and GS-6779 or Placebo in virally suppressed participants with CHB

- GS-2829 dose or Placebo
- GS-6779 dose or Placebo
- ▲ PBMC for Biomarker Cellular Assays
- ◊ Serum for HBV-Targeting Antibody Measurements
- ✗ Whole Blood for Biomarker Analysis
- HBV Neutralizing Antibody and Antivector Antibody Assessment
- △ HBV Viral Biomarkers (Phase 1b only)
- HBV Genomic Sequencing (Phase 1b only)
- HBV Genotyping (Phase 1b only)

** Day 141, Day 197 and Day 225 visits are only required for female participants of childbearing potential

CHB = chronic hepatitis B; HBV = hepatitis B virus; HP = healthy participant; PBMC = peripheral blood mononuclear cell
Note: A follow-up phone call will be performed on Days 2, 3, 30, 31, 58, 59, 86, and 87.

Figure 4. Schema for Cohorts 7 and 8 (Six Total Doses)

CHB = chronic hepatitis B; HBV = hepatitis B virus; HP = healthy participant; PBMC = peripheral blood mononuclear cell. Note: A follow-up phone call will be performed on Days 2, 3, 30, 31, 58, 59, 86, 87, 114, 115, 142, and 143..

STUDY PROCEDURES TABLES

Table 1. Schedule of Assessments, Phase 1a – Cohorts 1 and 2 (Two Total Doses)

Study Period	Screen	Active Dosing					Safety Follow-up								
		Baseline Day 1	Day 8	Day 15	Day 29	Day 57	Day 64	Day 71	Day 85	Day 113 ^a	Day 141	Day 169 ^a	Day 197 ^a	Day 225	ET
Study Day															
Visit Window (Days)	45 Days	N/A	± 1	± 1	± 3	± 3	± 1	± 1	± 3	± 7	± 7	± 7	± 7	± 7	N/A
Study Weeks		1	1	2	4	8	9	10	12	16	20	24	28	32	
Dosing (PBO or IP) ^b		X				X									
Written informed consent; I/E criteria; medical history	X														
Adverse events and concomitant medications	X	X	X	X	X	X	X	X	X	X	X	X	X	X	X
General Assessments and Laboratory Assessments															
Complete physical examination ^c	X	X				X								X	X
Symptom-directed physical examination ^d			X	X	X		X	X	X		X				
HIV-1, HBV, and HCV testing	X	X ^c				X ^{c,e}								X ^e	X
Height	X														
Weight	X	X				X								X	X
12-lead ECG	X													X	X
Vital signs	X	X ^f	X	X	X	X ^f	X	X	X		X			X	X
Urinalysis	X	X ^c		X	X	X ^c		X	X		X			X	X
Hematology ^g	X	X ^c		X	X	X ^c		X	X		X			X	X
FSH ^h	X														
Serum pregnancy test ⁱ	X	X ^c			X	X ^c			X	X	X	X	X	X	X
Urine pregnancy test ⁱ		X				X									

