Immunology and Biomarkers																								
PBMC collection for biomarker cellular assays		X ^c	X					X ^c	X	X	X	X	X	X				X						
Serum collection for HBV-targeting antibody measurements		X ^c			X ^c		X ^c		X ^c		X ^c		X ^c				X		X					X
Whole blood collection for biomarker analysis		X ^c					X ^c	X	X ^c	X	X ^c	X	X ^c		X									X
Clinical Virology																								
HBV neutralizing antibody and antivector antibody assessment		X ^c		X	X ^c		X ^c		X ^c		X ^c		X ^c			X		X			X		X	X
HBV viral biomarkers ^{o,l}		X ^c		X	X ^c		X ^c		X ^c		X ^c		X ^c			X		X			X		X	X
HBV genomic sequencing ^l		X ^c			X ^c		X ^c		X ^c		X ^c		X ^c			X		X			X		X	X
HBV genotyping ^l	X	X ^c																						

DNA = deoxyribonucleic acid; ECG = electrocardiogram; ET = early termination; FSH = follicle-stimulating hormone; HBcrAg = hepatitis B core-related antigen; HBeAg = hepatitis B e antigen; HBsAg = hepatitis B surface antigen; HBV = hepatitis B virus; HCV = hepatitis C virus; HDV = hepatitis D virus; HIV-1 = human immunodeficiency virus type 1; I/E = inclusion/exclusion; IP = investigational product; N/A = not applicable; PBMC = peripheral blood mononuclear cell; PBO = placebo; RNA = ribonucleic acid; Screen = screening

- a These visits are only required for pregnancy testing for women of childbearing potential. Participants who are able to access an at-home urine pregnancy test from the clinical site may conduct their pregnancy test at home and will be contacted by site staff to confirm the result. If urine pregnancy results are equivocal or positive, a serum pregnancy test will be required.
- b Participant shall receive the appropriate investigational product or PBO, as detailed in Section 5.3 and [Table 8](#). Participants in Cohort 7 will be monitored in the clinic for at least 2 hours following each dose of investigational product. Participants may be required to remain in the clinic for additional observation at the discretion of the investigator. Participants will receive a follow-up phone call for 2 consecutive days following each dose to review protocol restrictions, adverse events, any concomitant medication usage, and completion of participant diaries.
- c Collection of vital signs, physical examinations, and blood/urine samples should be completed prior to investigational product administration.
- d Symptom-driven physical examinations shall be performed as deemed necessary.
- e At the discretion of the investigator.

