6.6.1. Assessments for End of Study

A participant who completes the study will have an end of study visit for assessments and procedures specified in [Table 1](#), [Table 2](#), and [Table 3](#).

6.7. **Sample Storage**

Stored biological samples may be used by Gilead or its research partner for future testing to provide additional data to answer questions that relate to the main study. At the end of this study, these samples may be retained in storage by Gilead for up to 20 years or per country requirements. **CCI**
[REDACTED]

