- n Participants will be asked to record potential vaccine reactions based on solicited events via diary for 7 days following each administration of investigational product. Review of participant reactogenicity data will occur at each visit after vaccination up to 7 days postdose or beyond for cases with ongoing events after 7 days postdose.
- o To include the assessments of: HBV DNA, quantitative HBsAg, anti-HBsAg antibody, HBcrAg, HBeAg, HBV RNA.
- p Phase 1a: HBV testing is for HBsAg with reflex to HBV DNA, and hepatitis B core antibody. Phase 1b: HBV testing is for HBsAg, hepatitis B core antibody, HBV DNA, and quantitative HBsAg.

Table 12-3. Schedule of Assessments, Phase 1a – Cohort 8 and Phase 1b - Cohort 7 (Six Total Doses)

Study Period	Screen	Active Dosing												Safety Follow-up								
		Base-line Day 1	Day 8	Day 15	Day 29	Day 43	Day 57	Day 71	Day 85	Day 99	Day 113	Day 127	Day 141	Day 148	Day 155	Day 169	Day 197 ^a	Day 225	Day 253 ^a	Day 281 ^a	Day 309	ET
Visit Window (Days)	45 Days	N/A	±1	±1	±3	±1	±3	±1	±3	±1	±3	±3	±3	±3	±7	±7	±7	±7	±7	±7	±7	N/A
Study Weeks		1	1	2	4	6	8	10	12	14	16	18	20	21	22	24	28	32	36	40	44	
Dosing (PBO or IP) ^b		X			X		X		X		X		X									
Written informed consent; I/E criteria; medical history	X																					
Adverse events and concomitant medications	X	X	X	X	X	X	X	X	X	X	X	X	X	X	X	X	X	X	X	X	X	
General Assessments and Laboratory Assessments																						
Complete physical examination ^c	X	X			X		X		X		X		X								X	X
Symptom-directed physical examination ^d			X	X		X		X		X		X		X	X	X		X				
HIV-1 testing	X																				X ^e	X
HBV testing ^f	X	X ^e						X ^{cc}													X ^e	X
HCV testing	X																				X ^e	X
HDV testing ^g	X																					
Height	X																					
Weight	X	X			X		X		X		X		X								X	X
12-lead ECG	X							X				X									X	X
Vital signs	X	X ^f		X	X ^f	X	X ^f	X	X ^f	X	X ^f	X	X ^f	X	X	X		X			X	X
Urinalysis	X	X ^e			X ^e		X ^e	X	X ^e	X	X ^e	X	X ^e		X	X		X			X	X
Hematology ^g	X	X ^e		X	X ^e	X	X ^e	X	X ^e	X	X ^e	X	X ^e		X	X		X			X	X
FSH ^h	X																					
Serum pregnancy test ⁱ	X	X ^e			X ^e		X ^e		X ^e		X ^e		X ^e			X	X	X	X	X	X	X

Study Period	Screen	Active Dosing													Safety Follow-up								
		Base-line Day 1	Day 8	Day 15	Day 29	Day 43	Day 57	Day 71	Day 85	Day 99	Day 113	Day 127	Day 141	Day 148	Day 155	Day 169	Day 197 ^a	Day 225	Day 253 ^a	Day 281 ^a	Day 309	Day 309	ET
Study Day																							

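### Protocol 6.4.5.3 makes Days 169, 225 and 309 pregnancy-test-only in Cohorts 7 and 8, while Table 3 schedules general follow-up on those days

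*Protocol*

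**What the plan says.** Protocol Section 6.4.5.3 lists follow-up days separately for Cohorts 1 to 2, 3 to 6 and 7 to 8. For Cohorts 7 and 8 it says that "Day 169, Day 197, Day 225, Day 253, Day 281, and Day 309 are required only for pregnancy testing for women of childbearing potential".

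Protocol Table 3, the schedule for these two cohorts, carries the same restriction in footnote a: "These visits are only required for pregnancy testing for women of childbearing potential". Its header attaches the footnote to Days 197, 253 and 281 only. Days 169, 225 and 309 are unmarked. SAP Table 12-3 has the same header. It schedules vital signs, urinalysis and hematology on all three unmarked days, and a complete physical examination, weight and 12-lead ECG on Day 309.

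Other places that treat these days as general follow-up:

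- Synopsis, Duration of Intervention: all participants are followed for safety, "through Day 253 for Cohorts 3, 4, 5, and 6; and Day 309 for Cohorts 7 and 8".
- Protocol Section 6.6.1: "A participant who completes the study will have an end of study visit for assessments and procedures specified in" the schedule tables. The last scheduled day in Table 3 is Day 309.
- Protocol Table 6: ELISpot, HBV-specific antibody and immune complex samples on Days 169 and 225.
- SAP Tables 3-1 and 3-2: Days 169, 225 and 309. SAP Table 3-3: Days 169 and 225. SAP Table 3-4: Day 309.

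Protocol Sections 3.2 and 6.5 point the same way by implication only.

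For the other cohorts the text and tables agree. The note to Figure 2 (Cohorts 1 and 2) reads "Day 113, Day 169 and Day 197 visits are only required for female participants of childbearing potential", and the note to Figure 3 (Cohorts 3 to 6) reads "Day 141, Day 197 and Day 225 visits are only required for female participants of childbearing potential". Both match 6.4.5.3 and footnote a of Tables 1 and 2.

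**The concern.** Both statements cannot hold for Days 169, 225 and 309. Cohorts 7 and 8 receive the most injections and were added to study a third dose of each vector, so their follow-up after the last dose is what those cohorts are there to supply.

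If a site let 6.4.5.3 override Table 3, participants not of childbearing potential would have no required clinic visit after Day 155. Women of childbearing potential would need only pregnancy tests to Day 309, possibly done at home. The later scheduled laboratory tests (part of the primary endpoint), the vital signs, the last two ELISpot points (secondary endpoint) and the Day 309 ECG would not be required. In Cohort 7 no viral biomarker sample would be required after the sixth injection, because the Day 141 sample is taken before dosing. Change in HBsAg after that injection, an exploratory endpoint, would then go unobserved.

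Protocol Section 8.3.2 and SAP Section 3.6.1 say that missing data are in general not imputed, so visits lost this way would not be recovered in the analysis.

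**Working it through.** There is no stated figure to reproduce. The check compares day lists and counts visits.

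**1. Position of the listed days relative to the last dose.** Last-dose days are from Protocol Section 6.5; the offset is listed day minus last-dose day.

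| Cohorts | Last dose | Days listed in 6.4.5.3 | Offset (days) | Days with footnote a |
|---|---|---|---|---|
| 1–2 | Day 57 | 113, 169, 197 | 56, 112, 140 | 113, 169, 197 (Table 1) |
| 3–6 | Day 85 | 141, 197, 225 | 56, 112, 140 | 141, 197, 225 (Table 2) |
| 7–8 | Day 141 | 169, 197, 225, 253, 281, 309 | 28, 56, 84, 112, 140, 168 | 197, 253, 281 (Table 3) |

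The tables use one pattern throughout: pregnancy-only visits at +56, +112 and +140. Only the Cohorts 7–8 list in 6.4.5.3 adds +28, +84 and +168, which the SAP labels FU-WK4, FU-WK12 and FU-WK24.

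**2. Could the sentence just list every pregnancy test day?** Section 6.4.5.3 calls for testing every 28 days after treatment, which gives six days per schedule. For Cohorts 1–2 the sentence leaves out Days 85, 141 and 225 (57 + 28, + 84, + 168). For Cohorts 3–6 it leaves out Days 113, 169 and 253 (85 + 28, + 84, + 168). So in those cohorts it names only the pregnancy-only visits, and the same wording governs Cohorts 7–8. The text calls 3, 3 and 6 of the six days pregnancy-only; the tables mark 3, 3 and 3.

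**3. Length of required clinic follow-up.** Table 3: 309 − 141 = 168 days, or 24 weeks. With Days 169, 225 and 309 removed, the last general visit is Day 155: 155 − 141 = 14 days.

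**4. Scheduled visits in Cohorts 7–8 after Day 141**, with and without those three days. I read the cohort columns of SAP Table 3-1 in the same order as in Tables 3-2 to 3-4. Early termination visits and the Day 141 postdose vital signs are not counted.

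| Assessment | Source | Days scheduled | Days left | Count |
|---|---|---|---|---|
| Laboratory tests | SAP Table 3-1 | 155, 169, 225, 309 | 155 | 4 to 1 |
| Vital signs | SAP Table 3-2 | 148, 155, 169, 225, 309 | 148, 155 | 5 to 2 |
| ELISpot | SAP Table 3-3 | 155, 169, 225 | 155 | 3 to 1 |
| Viral biomarkers, Cohort 7 | SAP Table 3-1 | 169, 225, 309 | none | 3 to 0 |
| ECG | SAP Table 3-4 | 309 | none | 1 to 0 |

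**5. All postbaseline visits.**

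- Laboratory tests: 10 visits from Day 15 to Day 141, so 10 + 4 = 14, falling to 10 + 1 = 11.
- Vital signs: the same 10, so 10 + 5 = 15, falling to 10 + 2 = 12.
- ELISpot: 7 visits from Day 57 to Day 141, so 7 + 3 = 10, falling to 7 + 1 = 8.

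**6. Participants.** Two cohorts of about 10, each with 8 active and 2 placebo: 20 in all, 16 active and 4 placebo. The number not of childbearing potential is not given, so it can be anywhere from 0 to 20.

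**The case against.** The strongest reply is that the harm needs a site to let one sentence under a pregnancy-testing heading override the schedule that governs everything else. Section 6 says "The study procedures to be conducted for each participant enrolled in the study are presented in tabular form in" Tables 1 to 3. The sections on vital signs, laboratory tests, viral biomarkers, biomarker samples, posttreatment visits and the end of study visit each point to those tables. Section 9.1.7 ties data capture to the schedule, and Section 6.5 plans follow-up visits for all participants. The six days are exactly 141 + 28k for k = 1 to 6, which suggests that the full list of test days was entered where a shorter list was meant. Even on the literal reading, adverse event collection continues for 24 weeks (Sections 7.3.2 and 7.3.3), Day 155 laboratory and ELISpot samples remain, and 11 of 14 postbaseline laboratory visits are kept. The study is descriptive, with no formal testing.

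Most of this stands as an argument about likelihood: a site is more likely to follow Table 3. It does not remove the contradiction. The sentence still restricts attendance on three days that the schedule treats as general visits, none of the references to the tables is a precedence rule, and about 15 Phase 1b sites have to interpret the text. A drafting slip would explain the conflict but would leave it in force. Section 6.4.1 mentions ECG recording only at screening, with a reference to the tables. That leaves the Day 309 ECG less clearly supported in the text than the other assessments, but does not affect the rest of the point.

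**Conclusion.** The concern holds. For Cohorts 7 and 8 the current protocol text contradicts its own schedule on Days 169, 225 and 309; Days 197, 253 and 281 agree. The conflict is not an effect of text extraction or of the amendment log: the headers of Protocol Table 3 and SAP Table 12-3 agree with each other, and Protocol Table 6 and the SAP visit tables, listed separately, use the same days.

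The size depends on a site following 6.4.5.3 over Table 3, a reading that is possible but less likely. In that case the loss reaches up to about 20 planned participants in the two longest-dosed cohorts and takes away the scheduled general assessments beyond two weeks after the last dose. Without that condition nothing is lost, but the instruction to sites remains ambiguous. This is an operative attendance rule, so it should be fixed, even though the likely effect is modest.

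**What to change.** Reconcile the Cohorts 7–8 day list in Section 6.4.5.3 with Table 3 footnote a, Table 6, the synopsis, Section 6.6.1, and SAP Tables 3-1 to 3-4 and 12-3. One statement should then say who must attend Days 169, 225 and 309 and for which assessments. Which text reflects the intended schedule is for the sponsor to settle. Tell the sites the outcome, including any that have participants already past Day 155.

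If the change is made in 6.4.5.3, it is one sentence and needs no new analyses. It needs the usual ethics committee submission and documented approval before use (Protocol Sections 9.1.3 and 9.2.1) and a note to sites.
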